**Disclosure Statement:**

This is a double-blind, parallel-group study of ETX-018810 and placebo in subjects with DPNP. Treatment assignments will be blinded to the subjects, investigators and other study personnel, and all sponsor personnel that are involved in the conduct of the study or in the analysis of the study results. The subjects and investigators will be blinded to the study-specified baseline criteria that are necessary for randomization into the study.

**Number of Subjects:**

Approximately 410 subjects will be screened to achieve a minimum of 162 randomized subjects (81 per treatment group).

**Treatment Groups and Duration:**

Each subject will participate in the study for approximately 9 weeks, including a screening period of up to 4 weeks; a 4-week, double-blind treatment period; and a 1-week posttreatment follow-up period. Subjects will be randomized in a 1:1 ratio to receive 1000 mg of ETX-018810 or placebo BID for 4 weeks.

**Statistical Analysis Plan:**

The analysis populations were defined as:

- Safety Population - All subjects who received at least 1 dose of study treatment.
- Intent-to-treat (ITT) Population - All randomized subjects who received at least 1 dose of study treatment.
- Modified intent-to-treat (mITT) Population - All subjects in the ITT population who had at least 4 postbaseline measurements for the Pain Intensity Numeric Rating Scale (PI-NRS) in the eDiary.

The mITT population was used for the primary analysis of the primary efficacy endpoint and for all other eDiary efficacy endpoints; the ITT population was used for the analyses of the secondary efficacy endpoints. The safety population was used for the safety analyses.

Continuous data were summarized using descriptive statistics (e.g., mean, standard deviation), and categorical data were summarized using counts and percentages.

For the PI-NRS and DSIS (for which scores were completed daily in the eDiary), the weekly average was the mean of the non-missing scores for the 7-day period; the weekly average was calculated if at least one score was recorded for the week.

The treatment comparison for the change from baseline at Week 4 was estimated using a Mixed Model Repeated Measures (MMRM), which included the baseline score as a covariate; treatment group, visit (week), and the treatment-by-visit (week) as fixed effects; and a repeated structure that acknowledged the visits within a subject using an unstructured covariance structure. The Kenward-Rogers (1997) approximation was used to estimate the denominator degrees of freedom. The estimate, standard error, 90% CI, and associated p-value (2-sided) were presented.

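### The primary Week 4 pain model drops treated subjects with 1 to 3 diary scores that it could use, and the supplied synopsis names no ITT run to set beside it

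*Combined protocol and SAP*

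**What the plan says.** All of the relevant text is in the synopsis of the combined protocol and SAP, under Statistical Analysis Plan.

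- **ITT set:** "All randomized subjects who received at least 1 dose of study treatment".
- **mITT set:** "All subjects in the ITT population who had at least 4 postbaseline measurements for the Pain Intensity Numeric Rating Scale (PI-NRS) in the eDiary".
- **Primary analysis:** "The mITT population was used for the primary analysis of the primary efficacy endpoint".
- **Use of ITT:** "the ITT population was used for the analyses of the secondary efficacy endpoints". The same sentence also gives mITT to all other eDiary efficacy endpoints, so secondary diary endpoints fall under both sets. On neither reading does ITT cover the primary Week 4 comparison.
- **Weekly average:** "the weekly average was calculated if at least one score was recorded for the week".
- **Model:** an MMRM over weeks with baseline score as covariate and unstructured covariance. Of the output the synopsis says: "The estimate, standard error, 90% CI, and associated p-value (2-sided) were presented".

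Elsewhere in the synopsis, Number of Subjects plans at least 81 randomised per arm. Overall Design requires diary entries on at least 5 of the 7 days before baseline, and has site staff contact subjects who are not complying with study procedures.

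**The concern.** Randomisation makes the two arms comparable at the start. A set chosen by the number of diary scores recorded afterwards need not stay comparable, because treatment can affect that number through very early stopping. If the arms lose different numbers or different kinds of subjects, the Week 4 difference can shift towards the arm that loses more of its poor early responders.

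The rule is also hard to square with the rest of the plan. One score is enough for a weekly average, yet three scores in the whole treatment period are not enough to enter the model. What is at stake is whether a reader can tell that the exclusions were harmless. With neither an ITT run nor a count by arm, that cannot be judged.

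**Working it through.** **Who is removed.**

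- A treated subject with no post-baseline score adds nothing to the MMRM under either set.
- A treated subject with 1 to 3 scores has at least one weekly average, and has a baseline value because of the 5-of-7-day run-in. This subject could enter the model and is removed only by the mITT rule.
- A subject with four scores in Week 1 and none later is kept, with no Week 4 value. The MMRM handles that subject by assuming missingness at random. Adding those with 1 to 3 scores needs the same assumption and no other.

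**Inputs.** The supplied text gives no effect size, SD, power, dropout rate or exclusion rate, so there is no plan figure to reproduce. Only 81 per arm comes from the document. Assumed:

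- Week 4 residual SD 2.1.
- Residual SD either constant at 2.1 or rising from 1.2 at Week 1 to 2.1 at Week 4.
- Adjacent-week correlation 0.85.
- Excluded subjects have a Week 1 average only, and are g = 1.0 to 1.5 points worse at Week 1 than those retained in their arm.

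**Formulas.** Let d be active minus placebo exclusions, h the true Week 4 gap between excluded and retained subjects (g and h the same in both arms), and f = 0.85³ × (Week 4 SD / Week 1 SD).

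- f = 0.614 for constant SD, and 0.614 × 2.1/1.2 = 1.075 for rising SD.
- SE = 2.1 × √(2/81) = 0.33, taken as 0.34.
- mITT error = h × d/81, in favour of active.
- ITT error = (f × g − h) × d/81, against active.
- Chance of a false finding for active, if read from the 90% CI = 1 − Φ(1.645 − shift/0.34).

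**Case 1: the Week 4 outcome follows from Week 1 (h = f × g).** ITT error is zero. For mITT, the low end is g = 1.0 with constant SD and the high end is g = 1.5 with rising SD.

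| Exclusions, active v placebo | Shift (points) | Shift (SE) | False-finding rate (5.0% if no shift) |
|---|---|---|---|
| 2 v 1 | 0.008 to 0.020 | 0.02 to 0.06 | 5.2% to 5.6% |
| 5 v 1 (stress) | 0.03 to 0.08 | 0.09 to 0.23 | 6.0% to 7.9% |
| 8 v 2 (stress) | 0.05 to 0.12 | 0.13 to 0.35 | 6.5% to 9.8% |

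- Reversed imbalances shift against active: 1 v 5 gives 3.0% to 4.1%, and 2 v 8 gives 2.3% to 3.8%.
- A shift of 0.25 SE (0.085 points) needs 0.085/0.020 to 0.085/0.0076, that is 5 to 12 net extra exclusions.
- With correlation 0.70 to 0.95, each net exclusion moves 0.004 to 0.028 points.
- A 4,000-replicate simulation agreed. For 8 v 2 with g = 1.5, mITT was off by 0.068 (constant SD) and 0.119 (rising SD) in favour of active, and ITT was within 0.002 of zero.
- A harsher simulation dropped only the worst Week 1 responders in the active arm (SD 2, Week 1 to Week 4 correlation 0.6, no true effect). The mITT shift was 0.04, 0.06, 0.12 and 0.22 points for 1, 2, 4 and 8 exclusions.

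**Case 2: the early gap resolves (h = 0).** mITT error is zero. For 8 v 2 with g = 1.5, ITT is off by 1.5 × 0.614 × 6/81 = 0.07 to 1.5 × 1.075 × 6/81 = 0.12, against active. If h is half of f × g, the two errors are equal and opposite, at 0.03 to 0.06.

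**Case 3: equal counts, unequal gaps.** With 3 v 3 and equal gaps the shift is zero. With g = 1.5 in the active arm and 0 in placebo, mITT shifts by 1.5 × f × 3/81 = 0.03 to 0.06.

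**Case 4: a Days 1 to 3 average understates a full week's improvement by 0.3 to 0.6 points.** With h = f × g, ITT is off by understatement × f × d/81, against active: 0.002 to 0.008 points per net exclusion, and 0.01 to 0.05 for 8 v 2.

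**The case against.** The strongest reply has four parts.

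**ITT is not shown to be less biased.** A reader might infer that mITT favours the drug and that ITT corrects it. The documents do not support this. They give no exclusion counts, so even the direction is unknown, and Case 2 shows that mITT can be the more accurate set. This part stands, and it is why both results should be shown.

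**A minimum-score rule has a rationale.** Pain scores are entered in the evening and cover the previous 24 hours, while the first dose is taken in the clinic on Day 1. If a Day 1 score counts as post-baseline, which the supplied text does not settle, it may largely describe time before dosing, and the model would treat it as a full weekly average. This stands in part. The rule as written does not require the four scores to fall in one week or near Week 4.

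**Exclusions should be few.** The diary run-in, the compliance contact and the blinding ("Treatment assignments will be blinded to the subjects, investigators and other study personnel") all help, and the Rationale cites Phase 1 tolerability. This stands as to size, although none of it prevents early stopping for tolerability or lack of effect. Nor is the early termination visit evidence of such stopping; it is a general provision.

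**The analysis may exist, or may already be done.** A reader might infer that no ITT analysis of the primary endpoint was planned. Only a synopsis was supplied, so that does not follow. Its statistical section is in the past tense, which suggests that the data may have been analysed. Replacing the primary set would then be a post hoc change. This stands, and the fix allows for it.

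**Conclusion.** The point holds as a modest, cheaply closed gap. The primary set rests on a post-randomisation count that discards usable data and does not secure the endpoint, and the supplied text names no ITT run of the analysis.

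The expected shift is small, about 0.01 to 0.02 points per net extra exclusion under the assumed gap, SD and correlation. The shifts near 0.1 points come from stress cases for which the documents offer no evidence. Equal counts by arm would not by themselves show that the exclusions were harmless; the excluded subjects must also differ from those retained by the same amount in each arm. ITT's smaller error depends on the Week 4 outcome following from the Week 1 value.

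The case for ITT is that it stays closer to the randomised groups and adds no assumption beyond the one that the MMRM already makes. Nothing here shows the primary result to be invalid.

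**What to change.** 1. Run the same Week 4 PI-NRS MMRM on the ITT set already defined, as randomised, with every subject who has at least one post-baseline weekly average. Report it beside the mITT result.
2. Tabulate subjects with 0 and with 1 to 3 post-baseline scores by arm, with the reason and the scores available.
3. If the data are still blinded, make ITT the primary set and mITT supportive. If they are unblinded, keep mITT as the prespecified primary result and show ITT beside it.

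If the full SAP already contains the ITT run, only the table and a cross-reference are needed.

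**Cost:** some SAP wording, one more run of an existing model, and one table. The ITT estimate may be less favourable, and for the added subjects the Week 1 average may rest on only a few early scores. Subjects with no post-baseline score are not helped by either set; an imputation sensitivity analysis for them is optional and a separate matter.

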**Table S-1: Study Objectives and Endpoints**

Objectives	Endpoints
Primary	

 
To evaluate the efficacy of ETX-018810 on neuropathic pain via daily pain measurements in subjects with diabetic peripheral neuropathic pain (DPNP)
 
	
 
Change from baseline to Week 4 in the weekly average of the daily pain score as derived from the subject's responses on the Pain Intensity Numerical Rating Scale (PI-NRS)
 

Secondary	

 
To evaluate the efficacy of ETX-018810 on additional measures of pain and disability
 
	
 
Response rate, defined as a <math>\geq 50\%</math> reduction from baseline to Weeks 1, 2, 3, and 4 in the weekly average of the daily pain score
 
Response rate, defined as a <math>\geq 30\%</math> reduction from baseline to Weeks 1, 2, 3, and 4 in the weekly average of the daily pain score
 
Change in the weekly average of the daily pain score from baseline to Weeks 1, 2, and 3
 
Response rate on the Clinical Global Impression of Change (CGIC) scale at Week 4, defined as the proportion of subjects who are “much improved” or “very much improved”
 
Response rate on the Patient Global Impression of Change (PGIC) scale at Week 4, defined as the proportion of subjects who are “much improved” or “very much improved”
 
Change in the weekly average of the daily sleep score on the Daily Sleep Interference Scale (DSIS) from baseline to Weeks 1, 2, 3, and 4
 
Change in the Brief Pain Inventory (BPI) – Interference Scale from baseline to Week 4
 
Change in the BPI-Pain Scale from baseline to Week 4
 
Amount and pattern of acetaminophen use
 

 
To investigate the safety and tolerability of ETX-018810 in subjects with DPNP
 
	
 
Nature, frequency, and severity of nonserious and serious treatment-emergent adverse events (TEAEs)
 
Frequency of discontinuations due to TEAEs or death
 
Nature, frequency, and severity of posttreatment adverse events (AEs)/serious adverse events (SAEs)
 

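### Does a 90% confidence interval beside a two-sided p-value, with no stated significance level, leave the primary result open to two readings?

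*Combined protocol and SAP*

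**What the plan says.** Table S-1 gives one primary endpoint: "Change from baseline to Week 4 in the weekly average of the daily pain score", derived from the PI-NRS. The synopsis section headed Statistical Analysis Plan compares the arms at Week 4 with a mixed model for repeated measures (unstructured covariance, Kenward-Roger degrees of freedom) and closes with the outputs: "The estimate, standard error, 90% CI, and associated p-value (2-sided) were presented".

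The Number of Subjects section gives about 410 screened and at least 162 randomized, 81 per group. Treatment Groups and Duration adds the allocation: "Subjects will be randomized in a 1:1 ratio to receive 1000 mg of ETX-018810 or placebo BID for 4 weeks". Neither section gives a significance level, power, target difference or standard deviation. The supplied text contains no hypothesis statement and no rule for calling the trial positive. No redaction is visible in these sections. All the supplied text comes from the synopsis.

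**The concern.** A two-sided p-value is usually read against 0.05, and the interval that matches that test is a 95% interval. The plan pairs the p-value with a 90% interval, which matches a two-sided 10% test (one-sided 5%). With no level stated, a result at p = 0.06 could be described as an interval excluding zero or as a test that missed 5%. If the interval were taken as the criterion, the two-sided false-positive rate would be 10%. The worry is that the wording of the main conclusion could be chosen after the data are seen.

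**Working it through.** **Inputs.** From the synopsis: 90% interval, two-sided p-value, 81 per group, 1:1 allocation. Assumed, because the documents do not give them: significance level (0.05 or 0.10, two-sided), standardized effect d, no dropout, and 100 to 160 degrees of freedom for the interval checks.

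**The plan's own figure.** The 162 cannot be reproduced, because level, power, effect and SD are all absent. It can only be solved backwards, with d = (z for the level + z for the power) × √(2/81), where √(2/81) = 0.1571. At 80% power:

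- two-sided 0.05: (1.960 + 0.842) × 0.1571 = 0.440
- two-sided 0.10: (1.645 + 0.842) × 0.1571 = 0.391

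The noncentral t distribution gives 0.443 and 0.392. Since no target effect is stated, the sample size does not show which level was used, and it rules out neither.

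**Do the interval and the p-value conflict?** In standard-error units the limits are t ± critical value. With 130 degrees of freedom the critical values are 1.657 (90%) and 1.978 (95%).

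| Two-sided p | 90% interval (SE units) | 95% interval (SE units) |
|---|---|---|
| 0.06 | 0.24 to 3.55 | −0.08 to 3.88 |
| 0.08 | 0.11 to 3.42 | −0.21 to 3.74 |
| 0.101 | −0.005 to 3.31 | −0.33 to 3.63 |

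The 90% interval excludes zero when p is below 0.10 and includes it when p is above 0.10. The planned interval and the planned p-value therefore always agree with each other. The disagreement is between the planned 90% interval and a 5% threshold, and the documents do not contain that threshold.

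**Can a reader recover the 95% interval?** The ratio of critical values is 1.975/1.654 = 1.194 at 160 degrees of freedom and 1.984/1.660 = 1.195 at 100. Multiplying the 90% half-width by about 1.19 gives the 95% interval. The reported standard error gives the same answer as estimate ± about 1.97 to 1.98 SE.

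**How often does the choice of level matter?** With no effect, P(0.05 < p < 0.10) = 0.10 − 0.05 = 5%. Half of that favours placebo, so 2.5% favours the drug. The false-positive rate in the drug's favour is 5% at the two-sided 10% level and 2.5% at the two-sided 5% level. With a true effect (81 per group, 160 degrees of freedom, noncentral t):

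| Assumed d | Power at 5% | Power at 10% | Difference |
|---|---|---|---|
| 0.30 | 47.5% | 60.1% | 12.6 points |
| 0.40 | 71.6% | 81.3% | 9.7 points |
| 0.443 | 80.0% | 87.7% | 7.7 points |

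The last column is both the share of trials in which the level decides the reading and the power given up if 5% is imposed where 10% was intended.

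**The case for a change.** The strongest case for a change is that a plan should fix its decision rule in advance, and nothing supplied does so. The sample size does not reveal the level, and the label on the p-value does not point to a one-sided 5% test. If everyone takes 0.05 for granted, the interval does not match the test. If 10% is meant, the text should say so. For the assumed effects above, between about one trial in 8 (12.6%) and one in 13 (7.7%) would land where the level decides the reading. Naming the level takes one line.

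Part of this stands. The level is not stated, and a reader of the synopsis cannot tell which one applies. A report should name the level that was set before unblinding.

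The rest does not stand. A synopsis that describes the analysis briefly and in the past tense is weak evidence that no level was ever fixed. The plan also commits to showing the estimate, the standard error, the interval and the p-value together, so a borderline result cannot be hidden by quoting one of them. The 10% false-positive figure counts errors in both directions, whereas a wrongly positive trial concerns only the favourable half. Finally, the 90% interval is specified for the change-from-baseline model. The synopsis states no interval level for the responder and global-impression endpoints, so for those there is nothing to replace.

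**Conclusion.** The concern does not call for a change. The 90% interval and the two-sided p-value are each valid, agree with each other and are both reported. What is missing is the significance level, a detail that the analysts can supply from the level fixed before unblinding without altering the model, the estimate, the standard error or the p-value.

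Switching to a 95% interval with a two-sided 5% test would be a trade-off and not a correction. A two-sided 10% (one-sided 5%) criterion is defensible in a Phase 2 study. Moving from it to 5% halves the favourable false-positive rate from 5% to 2.5%, and at d = 0.40 it lowers power from 81.3% to 71.6%. Printing a 95% interval as well would change no result, since it is the 90% interval about 19% wider.

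The power figures rest on assumed standardized effects, 81 analysed per group and no dropout. The finding that no level is stated applies to the supplied synopsis text only.
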